### 5.3.1. Safety Variables

Safety measures that will be used in the study include adverse events (AEs), DLT, clinical laboratory test results, vital signs, electrocardiograms (ECGs) and ECHO/MUGA scanning.

#### Dose Limiting Toxicity (DLT)

Dose-limiting toxicity is defined as an AE during Cycle 1 (Cycle 2 for combination treatment) for a patient enrolled in Part A and Part B that is possibly related to the study drug and fulfills any one of the following criterion using the National Cancer Institute's Common Terminology Criteria for Adverse Events (NCI-CTCAE) Version 4.0:

- CTCAE Grade >3 nonhematologic toxicity. Exceptions will be made for:
  - Grade 3 febrile neutropenia without complications,
  - Grade 3 events of nausea, vomiting, diarrhea, transient electrolyte abnormalities, and constipation that can be controlled with optimal medical management within 48 hours, and
  - transient Grade 3 elevations of alanine transaminase (ALT) and/or aspartate aminotransferase (AST) lasting fewer than 8 days,
  - without evidence of other hepatic injury may not be considered a DLT if
  - agreed by the study investigator and Lilly CRP/CRS.
- Grade 4 neutropenia that lasts longer than 2 weeks
- Grade  $\geq 3$  thrombocytopenia complicated by hemorrhage
- Any hematologic toxicity that causes a cycle delay of >14 days
- Any other significant toxicity deemed by the primary investigator and Lilly clinical research personnel to be dose limiting (for example, any toxicity that is possibly related to the study medication that requires the withdrawal of the patient from the study during Cycle 1)

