7.2.3.2. Dose-Escalation Method

Part B will be initiated after the following criteria have been met:

- Acceptable safety results, which must include a minimum of 6 evaluable patients, and the PK profile from Part A monotherapy
- At least one of the 15 mg/kg combination arms has met the following DLT criteria: less than one third (that is, approximately 33.3% [minimum of 3 patients]) DLT rate. Only the combination arms in Part A that have met these criteria may be studied in Parts B and C.

In Part A, if the DLT rate is $> 1/3$ (that is, greater than 4 out of 12 patients) during Cycle 1 monotherapy, then the dose of olaratumab will be reduced to 10 mg/kg. In Part B, if the DLT rate is $> 1/3$ during Cycle 1 monotherapy, then the dose of olaratumab will be reduced to

15 mg/kg. In Part C, if the DLT rate is >1/3 during Cycle 1 combination therapy, then the dose of olaratumab will be reduced to 15 mg/kg.

If the DLT rate is >1/3 in the first cycle (Parts A and B Cycle 2, or Part C Cycle 1) of any of the chemotherapy arms, then appropriate dose de-escalation ([Table JGDN.7.3](#)) of olaratumab for that combination will occur.

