7.2.4. Dose Adjustments and Delays

In the event that a patient experiences a DLT or a DLT-equivalent (a DLT occurring in Cycle 3 or later of Parts A and B or Cycle 2 or later of Part C), treatment will be interrupted. Dosing can be resumed after resolution of the toxicity to baseline levels at the next lower dose level ([Table JGDN.7.3](#)) already deemed safe upon discussion with the Lilly CRP/CRS. For Grade 3/4 toxicities that are not dose-limiting, see Section [7.2.4.1.2](#) for hematologic toxicities and Section [7.2.4.1.3](#) for nonhematologic toxicities.

Table JGDN.7.3. Olaratumab Dose Levels and Adjustments for Olaratumab-related Toxicities

Dose at Enrollment	Dose Reduction		
	First	Second	Third
Dose level 3	20 mg/kg	15 mg/kg	10 mg/kg
Dose level 2	15 mg/kg	10 mg/kg	discontinue olaratumab
Dose level 1	10 mg/kg	discontinue olaratumab	

In the event of alteration of olaratumab therapy due to an olaratumab-related toxicity, chemotherapy need not be altered, and the planned chemotherapy schedule should be maintained. In the event that olaratumab treatment is discontinued for reason of toxicity, the patient should be discontinued from the study.

Similarly, olaratumab therapy should not be altered for chemotherapy-related toxicity, even if the chemotherapy dose is modified. In the event that chemotherapy is discontinued for reason of toxicity, the patient should be discontinued from the study.

To begin dosing at each cycle, the following criteria must be fulfilled:

- ANC $\geq 750/\text{mm}^3$
- Platelets $\geq 75,000/\text{mm}^3$
- Hemoglobin $\geq 8 \text{ g/dL}$
- Total bilirubin $\leq 1.5 \times \text{ULN}$
- AST and ALT $\leq 3.0 \times \text{ULN}$, or $\leq 5 \times \text{ULN}$ if the transaminase elevation is due to liver metastases
- Any nonhematologic toxicity that are NCI-CTCAE, v4.0 Grade <2 or equivalent severity to baseline

Treatment may be delayed for up to 14 days to allow a patient sufficient time for recovery from study drug-related toxicity.

The following information (in this section and the following subsections) pertains to dose modifications and delays for and management of AEs of concern, which may or may not be associated with olaratumab therapy, including the following:

- IRR (see Section [7.2.4.1.1](#))
- Hematologic toxicity (see Section [7.2.4.1.2](#))
- Nonhematologic toxicity (see Section [7.2.4.1.3](#))

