7.6.1. Evaluable Patients

Patients who withdraw from the study before receiving study drug(s) will be replaced and will not be included in the safety or efficacy assessments. Safety analyses will be conducted on all patients who have been exposed to study drug, regardless of whether they are deemed evaluable for other assessments.

Any patient from Parts A or B who is discontinued from the study before completing 1 cycle of olaratumab treatment will be deemed non-evaluable for assessment of olaratumab monotherapy, unless the patient experiences a DLT prior to withdrawal. Any patient who is discontinued from the study before completing 1 cycle of combination chemotherapy treatment (Cycle 2 for Parts A or B or Cycle 1 for Part C) will be deemed non-evaluable for assessment of a combination chemotherapy, unless the patient experiences a DLT or DLE-equivalent prior to withdrawal.

If a patient from Parts A or B is noncompliant during Cycle 1 due to reasons other than drug-related toxicity, he or she will be considered non-evaluable for olaratumab monotherapy and may be replaced. If a patient from Parts A or B is noncompliant during Cycle 2 or a patient from Part C is noncompliant during Cycle 1 due to reasons other than drug-related toxicity, he or she will be considered non-evaluable for combination chemotherapy and may be replaced.

Nonevaluable patients may be replaced to ensure that enough patients complete 1 cycle of olaratumab monotherapy or combination chemotherapy, unless accrual to that cohort has stopped due to a DLT.

Patients who are not evaluable for pharmacokinetics, but who complete 1 cycle of olaratumab monotherapy or 1 cycle of combination chemotherapy, may be replaced to ensure adequate PK data, unless accrual to that cohort has stopped due to a DLT.

8. Safety, Pharmacokinetic, Pharmacodynamic, and Efficacy Data Collection

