10 mg/kg (~12 pts)	Acceptable DLT level	10 mg/kg	Acceptable DLT level	10 mg/kg		
> 1/3 DLT (i.e. >4 of 12)		> 1/3 DLT				
Study stop/ reassess		Study stop or reassess				
a. In combination with any of the 3 chemotherapy regimens in Part A that have successfully passed the DLT criteria described above for Part A (doxorubicin or vincristine/irinotecan or high-dose ifosfamide per investigator discretion). b. Part A and B includes monotherapy treatment of Olaratumab in cycle 1 with the remainder being combination treatment. Part C includes combination treatment starting from Cycle 1.						

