#### DLT-Equivalent Toxicity

A DLT-equivalent toxicity is defined as DLT event occurring in Cycle 3 or later.

Adverse event-related variables are listed below:

- **Adverse event (AE)** is defined as any untoward medical occurrence in a patient administered a pharmaceutical product, without regard to the possibility of a causal relationship.
- **AEs of special interest (AESIs)**

AESI for olaratumab:

- Infusion-related reactions (IRRs)

Notes: Categories of AESI may be modified as the understanding of the safety of the investigational drug increases. The final list of categories will be maintained at both compound and study level and reported in the clinical study report (CSR).

- Infusion Related Reactions (IRR) and delayed hypersensitivity reactions analysis uses the current standard Medical Dictionary for Regulatory Activities (MedDRA) Standardised Medical Queries (SMQs) to search for relevant events. Treatment-emergent adverse events are characterized as follows:
  - Anaphylactic reaction SMQ (narrow or algorithm per MedDRA SMQ guide )
  - Hypersensitivity SMQ (narrow) excluding PTs specific to injection site reactions
  - Angioedema SMQ (narrow)
  - Event maps to Preferred Term (PT) of Infusion related reaction
  - Event maps to PT of Cytokine release syndrome.

Medical review of each case identified by the algorithm above will be conducted prior to unblinding. Considerations for narratives and final designations include family history, pre-existing conditions, concomitant meds (e.g., was epinephrine used to treat), ruling out other confounding causes such as bee stings and food allergies, timing of the event, mechanism or biologic plausibility, and number of administrations. Such cases that clearly have a cause other than study drug will be excluded from the analyses.

Time frame: a day of infusion will be considered for immediate IRRs (i.e. immediate hypersensitivity reactions ). The 6 days after an infusion will be considered for delayed hypersensitivity reactions (i.e. if olaratumab is administered on Day 1 events occurred on Days 2 to 7 are considered; if olaratumab is administered on Day 8 events occurred on Days 9 to14 are considered).

- **Consolidated AEs** are composite AE terms consisting of synonymous Medical Dictionary for Regulatory Activities (MedDRA) preferred terms (PTs) to allow meaningful interpretation of the AE data. Consolidated AE categories and PTs will be maintained at compound level and reported in the CSR.

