**Table JGDN.5.2. Analysis Populations**

Population	Definition	Analysis Type / Variable	Note
All Entered Patients	All patients who signed Inform Consent		
Safety Population	All entered patients who received any quantity of study drug	Baseline characteristics, concomitant medication, efficacy analyses, Safety, e.g. dosing/exposure, AE and resource utilization.	For efficacy analysis, patients will be grouped according to the assigned dose level cohort.
DLT-evaluable Population	Patients who complete Cycle 1 (Part A/B Cycle 2 for combination treatment) or discontinue due to a DLT prior to completing Cycle 1 treatment (Part A/B Cycle 2 for combination treatment)	DLT assessment/AE	For safety analysis, patients will be grouped according to the actual dose level received.

Abbreviations: AE = adverse event; DLT = Dose-Limiting Toxicity.

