## 5.13. Interim Analysis

No interim analyses are planned for this study.

Since this is a dose-finding study, data will be reviewed on a cohort-by-cohort basis during the study, until a tolerated dose of Olaratumab monotherapy will be identified in cycle 1 of Part A and Part B. DLTs will also be assessed within the combination therapy (Cycle 2 onward of Part A and B; Cycle 1 onward of Part C). Dose escalation and de-escalation are planned where decisions are based on DLT rates (see Figure JGDN.1). The starting dose in Part A is 15mg/kg and could de-escalate to 10 mg/kg if DLTs are observed. The dose in Part B will start at 20mg/kg and could de-escalate to the Part A identified tolerable Olaratumab dose. Part C will receive olartumab (20mg/kg) in combination with any of the 3 chemotherapy regimens from Cycle 1 onward (i.e. no olaratumab monotherapy in Cycle 1). The purpose of these cohort-by-cohort reviews is to evaluate the safety data at each dose level and determine if a DLT has been observed that would suggest a tolerated treatment combination has been met or exceeded. The investigators and the Lilly study team will make the determination regarding dose escalation based upon their review of the safety and tolerability data as described in the protocol.

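### The SAP's DLT and DLT-equivalent definitions were not extended to Part C: read literally, Part C Cycle 1 and Cycle 2 events fall in neither class

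*SAP*

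**What the plan says.** SAP 5.3.1 defines a DLT as "an AE during Cycle 1 (Cycle 2 for combination treatment) for a patient enrolled in Part A and Part B" that also meets the listed toxicity criteria. Part C is not named. The next entry reads "A DLT-equivalent toxicity is defined as DLT event occurring in Cycle 3 or later", with no distinction by part.

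The protocol treats Part C differently on both points. Section 7.2.3.2 has a rule that begins "In Part C, if the DLT rate is >1/3 during Cycle 1 combination therapy". Section 7.6.1 gives the evaluability window for combination treatment as "Cycle 2 for Parts A or B or Cycle 1 for Part C". The DLT definition in 7.2.3.1 is not limited to particular parts. Section 7.2.4 describes a DLT-equivalent as "a DLT occurring in Cycle 3 or later of Parts A and B or Cycle 2 or later of Part C".

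Other SAP passages also include Part C:

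- Section 5.13: "DLTs will also be assessed within the combination therapy (Cycle 2 onward of Part A and B; Cycle 1 onward of Part C".
- Figure JGDN.2 applies its >1/3 DLT step to a column whose heading includes Part C Cycle 1, and its footnote says "Part C includes combination treatment starting from Cycle 1".
- Table JGDN.5.2 describes the DLT-evaluable population as "Patients who complete Cycle 1 (Part A/B Cycle 2 for combination treatment) or discontinue due to a DLT". Only the Cycle 2 window is tied to Parts A and B, so Part C Cycle 1 is covered by implication.

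**The concern.** The definitions look like text left over from before Part C was added. Protocol amendment (b), dated 14-Feb-2018, introduced Part C. SAP Version 3, dated 26-Nov-2018, was issued partly to reflect it, yet 5.3.1 still names only Parts A and B. The planned olaratumab dose intensity in SAP 5.9.1 also lists only Parts A and B.

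Protocol 6.2.1 makes DLT one of the two components of the primary endpoint, and the primary objective is a recommended dose in combination. Part C gives olaratumab with chemotherapy from its first cycle, so its DLTs bear directly on that objective. SAP 5.9.2 promises DLTs and DLT-equivalents listed by cohort, and protocol 10.4 promises DLTs summarized at each dose level. Applied as worded, 5.3.1 would produce outputs with no Part C DLTs. Table JGDN.5.2 would meanwhile count Part C patients as DLT-evaluable, so they would be in the denominator with their events excluded from the numerator.

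**Working it through.** **Classification by part and cycle.** The plan states no figure to reproduce, so the check is to classify each combination of part and cycle under three rules:

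- the protocol windows (7.2.3.2 and 7.2.4);
- SAP 5.3.1 read literally;
- SAP 5.3.1 read leniently, with the reference to Parts A and B attached only to the Cycle 2 parenthesis.

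| Part and cycle | Protocol | SAP, literal | SAP, lenient |
|---|---|---|---|
| A and B, Cycle 1 | DLT | DLT | DLT |
| A and B, Cycle 2 | DLT | DLT | DLT |
| A and B, Cycles 3 and 4 | DLT-equivalent | DLT-equivalent | DLT-equivalent |
| C, Cycle 1 | DLT | neither | DLT |
| C, Cycle 2 | DLT-equivalent | neither | neither |
| C, Cycles 3 and 4 | DLT-equivalent | DLT-equivalent | DLT-equivalent |

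With three parts and four cycles there are 12 cells. The literal reading departs from the protocol in 2 of them and the lenient reading in 1. A third reading ignores the restriction by part and applies the Cycle 2 combination window to Part C. Part C Cycle 2 then becomes a DLT, where the protocol calls it a DLT-equivalent. All three readings depart from the protocol for Part C.

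**Size of Part C.** Parts B and C together enroll up to 45 (protocol 6.2). Part B is complete with at least 10 evaluable patients under protocol 7.2.3, or at least 12 under SAP 5.1.

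- 45 − 10 = 35, and 35/45 = 77.8%.
- 45 − 12 = 33, and 33/45 = 73.3%.

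Both are upper limits. The 45 is a maximum, and it counts enrolled patients while the 10 and 12 count evaluable ones.

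**Part C Cycle 1 DLTs left out on the literal reading.** With n evaluable patients, a true DLT rate p and independent patients, the expected number is n × p and the chance of at least one is 1 − (1 − p)^n. The documents give no rate, so p is assumed. The sizes 20 and 10 are also assumed, to show a smaller Part C.

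| n | p = 5% | p = 10% | p = 20% | p = 1/3 |
|---|---|---|---|---|
| 35 | 1.75 (83.4%) | 3.5 (97.5%) | 7.0 (99.96%) | 11.67 (>99.99%) |
| 33 | 1.65 (81.6%) | 3.3 (96.9%) | 6.6 (99.9%) | 11.0 (>99.99%) |
| 20 | 1.0 (64.2%) | 2.0 (87.8%) | 4.0 (98.8%) | 6.67 (99.97%) |
| 10 | 0.5 (40.1%) | 1.0 (65.1%) | 2.0 (89.3%) | 3.33 (98.3%) |

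For example, with n = 20 and p = 10%: 20 × 0.10 = 2.0, and 1 − 0.9^20 = 87.8%.

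These figures concern Cycle 1 only. The Cycle 2 gap is not sized, because the documents give neither a Cycle 2 event rate nor the number of Part C patients expected to reach that cycle.

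**The case against.** The strongest reply is that the Cycle 1 half depends on how one sentence is parsed. The reference to Parts A and B can be attached to the Cycle 2 parenthesis alone, which is how Table JGDN.5.2 is built, and Part C Cycle 1 then counts. SAP 5.13 and Figure JGDN.2 support that intent. DLTs also cannot be derived by program alone. One criterion and the transaminase exception rest on the judgement of the investigator and sponsor staff, and cohort reviews run under the protocol. An analyst would have to overlook all of this to list no Part C DLTs. Finally, DLT-equivalents feed only a listing with no threshold attached, the analyses are descriptive, and the event counts above address only the parse-dependent half.

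Much of this stands. The intended Cycle 1 rule can be inferred, and the counts are the exposure under a literal reading, not a forecast. But the reply leaves the Cycle 2 mismatch untouched: SAP 5.3.1 and protocol 7.2.4 disagree on either parse. Nor should a definition serving a primary endpoint component have to be reconstructed from a figure heading and a population table.

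**Conclusion.** The concern holds. On Part C Cycle 2 the SAP contradicts the protocol under any reading. On Part C Cycle 1 it contradicts the protocol, and its own later passages, when read literally. Up to 35 of the 45 patients in Parts B and C are exposed, if Part B stops at 10, every place is filled and no Part B patient is non-evaluable. The expected number of unlisted Cycle 1 DLTs ranges from 0.5 (10 evaluable patients, 5% rate) to 11.67 (35 patients, one-third rate), and all of these rates are assumptions.

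The consequence is confined to reporting. Dose decisions during the trial follow the protocol, and the events would remain in the treatment-emergent tables and the adverse event listing. No pooled Part B and C DLT rate is specified, so no dilution of such a rate is claimed. The point should be corrected before the final analysis, but it does not threaten trial conduct.

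**What to change.** In SAP 5.3.1, state the DLT window by part, as the protocol does: Cycle 1 monotherapy and Cycle 2 combination for Parts A and B, and Cycle 1 for Part C. State the DLT-equivalent window in the same way, following protocol 7.2.4: from Cycle 3 for Parts A and B, and from Cycle 2 for Part C. Name Part C in the DLT-evaluable row of Table JGDN.5.2. With these windows all 12 cells agree with the protocol and none is unclassified.

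Two neighboring points should be reconciled at the same time, and neither is needed for the conclusion above. The SAP gives the nonhematologic criterion as Grade >3 and protocol 7.2.3.1 gives Grade ≥3. This may be a typing or PDF slip, since every listed exception is Grade 3, so check the source file; no threshold is proposed here. Also, the 21-day limit in protocol 7.2.3.1 does not match the Cycle 2 window that 7.2.3.2 uses for Parts A and B.

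The cost is a few words in the SAP and a wording check in the protocol. No new data are needed and trial conduct does not change.

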6.2. Summary of Study Design

[figure not shown]
Study JGDN is a multicenter, dose-escalation, open-label Phase 1 pediatric safety clinical trial with 3 distinct components, Part A, Part B, and Part C.

Part A will consist of at least 12 evaluable pediatric patients. Given the expected diversity of age and body weight in the study population, this sample size is expected to provide the necessary amount of PK information in order to characterize the disposition of olaratumab in the pediatric population.

Patients will be treated for 1 cycle (21 days) of olaratumab monotherapy at 15 mg/kg on Day 1 and Day 8 (adult dose for which efficacy was observed in Study JGDG). If the patient does not experience a DLT in the first cycle of monotherapy, or meet any other criteria for discontinuation, the patient will then receive olaratumab (15 mg/kg) plus one of 3 standard chemotherapy regimens (doxorubicin or vincristine/irinotecan or high-dose ifosfamide per investigator discretion). Treatment will continue until disease progression or other discontinuation criteria are met.

During Cycle 1 monotherapy, if the DLT rate is >1/3 (that is, greater than 4 out of 12 patients), then the dose of olaratumab will be reduced to 10 mg/kg. If the DLT rate is >1/3 in the first cycle (Cycle 2) of any of the combination therapy arms, then appropriate dose de-escalation of olaratumab for that combination will occur. Another cohort with at least 3 patients will be studied for that combination with olaratumab at 10 mg/kg.

Part A of the study design is illustrated in [Figure JGDN.6.1](#).

Part A**Figure JGDN.6.1. Illustration of Part A of the study design.**

Part B will be initiated after the following criteria have been met:

- Acceptable safety results, which must include a minimum of 6 evaluable patients, and the PK profile from Part A monotherapy.
- At least one of the 15 mg/kg combination arms has met the following DLT criteria: less than one-third (that is, approximately ~33.3% [minimum of 3 patients]) DLT rate. Only the combination arms in Part A that have met these criteria may be studied in Part B.

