6.2.1. Primary Endpoint

Primary endpoint is defined as DLT and PK data exposure matching. The primary endpoint analysis will occur after the final patient enrolled has been evaluated for at least 2 cycles.

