7.2.3.1. Dose-Limiting Toxicity Determination and Maximum Tolerated Dose Definition

A DLT is defined as an adverse event (AE) during the first 21 days that is possibly related to the study drug and fulfills any one of the following criterion using the National Cancer Institute's (NCI) Common Terminology Criteria for Adverse Events (CTCAE) v 4.0:

- CTCAE Grade ≥ 3 nonhematologic toxicity. Exceptions will be made for:
 - Grade 3 febrile neutropenia without complications,
 - Grade 3 events of nausea, vomiting, diarrhea, transient electrolyte abnormalities, and constipation that can be controlled with optimal medical management within 48 hours, and
 - transient Grade 3 elevations of ALT and/or AST lasting fewer than 8 days, without evidence of other hepatic injury may not be considered a DLT if agreed by the study investigator and Lilly CRP/CRS.
- Grade 4 neutropenia that lasts longer than 2 weeks
- Grade ≥ 3 thrombocytopenia complicated by hemorrhage
- Any hematologic toxicity that causes a cycle delay of > 14 days
- Any other significant toxicity deemed by the primary investigator and Lilly clinical research personnel to be dose limiting (for example, any toxicity that is possibly related to the study medication that requires the withdrawal of the patient from the study during Cycle 1)

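### SAP 5.3.1 sets the automatic nonhematologic DLT threshold at Grade >3 where protocol 7.2.3.1 sets Grade ≥3, so the reported DLT endpoint could differ from the counts behind the dose decisions

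*SAP*

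**What the plan says.** Protocol 6.2.1 states: "Primary endpoint is defined as DLT and PK data exposure matching". Protocol 7.2.3.1 defines a DLT, and its first criterion is "CTCAE Grade ≥ 3 nonhematologic toxicity", followed by exceptions for certain Grade 3 events.

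SAP 5.3.1 repeats the list almost word for word, but its first criterion reads "CTCAE Grade >3 nonhematologic toxicity. Exceptions will be made for". The exceptions are the same as in the protocol: "Grade 3 febrile neutropenia without complications"; Grade 3 gastrointestinal and transient electrolyte events that are controlled within 48 hours; and short-lived Grade 3 ALT/AST rises. Further down the same SAP list, the thrombocytopenia criterion is printed with ≥3. The list ends with a discretionary criterion: "Any other significant toxicity deemed by the primary investigator and Lilly clinical research personnel to be dose limiting".

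Three other parts of the SAP rest on this definition. Section 5.3.1 defines a DLT-equivalent toxicity as a DLT event in Cycle 3 or later. Table JGDN.5.2 of the SAP admits to the DLT-evaluable population patients who finish the relevant cycle or stop early because of a DLT. Section 5.9.2 lists DLTs and DLT-equivalents by cohort.

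On dose decisions, SAP 5.13 says the investigators and study team decide "based upon their review of the safety and tolerability data as described in the protocol".

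**The concern.** The two documents give different thresholds for the same criterion, and the criterion belongs to one of the two components of the primary endpoint. A related Grade 3 mucositis or infection outside the exceptions is an automatic DLT under the protocol. Under the literal SAP text it is one only if the investigator and sponsor declare it.

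The SAP text also does not work on its own terms. An exception for a Grade 3 event has no effect on a rule that starts at Grade 4. The SAP's revision history names no change to the DLT threshold, so nothing suggests that the difference was intended.

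At stake is agreement between two counts: the one the team used to open parts and hold or reduce doses, and the one the study report presents as the primary endpoint. If they differ, the reported count could be the lower one, and the report would not explain why.

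**Working it through.** 1. **The plan's own boundary.** The protocol states its de-escalation rule in section 6.2 as "if the DLT rate is >1/3 (that is, greater than 4 out of 12 patients"). The smallest r with r/12 > 1/3 is r = 5, since 4/12 equals 1/3 exactly. The stated figure reproduces: 5 or more of 12.

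2. **The two criteria.** The protocol counts Grades 3, 4 and 5, less the exceptions. The literal SAP counts Grades 4 and 5. The difference is every non-excepted, possibly related Grade 3 nonhematologic event in the DLT window. The hematologic criteria and the discretionary criterion are unaffected.

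3. **Effect on a small arm.** Protocol 6.2 lets a Part A combination arm go forward if its DLT rate is below one-third in at least 3 patients. With 3 patients:
   - protocol count 1/3 = 33.3%, not below one-third;
   - the same patient not counted under the literal SAP: 0/3 = 0%, below one-third.

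4. **Effect on the denominator.** Suppose one of 3 patients stops early because of a Grade 3 nonhematologic event. Under the protocol that patient is evaluable and the rate is 1/3. Under the literal SAP, if the event is not declared dose limiting by discretion, the patient has neither finished the cycle nor stopped for a DLT. The patient leaves numerator and denominator, and the rate is 0/2.

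5. **How common Grade 3 is among such events.** The only grade split is protocol Table JGDN.5.2 (adult study JGDG). I summed the rows, leaving out neutropenia, anemia, thrombocytopenia and lymphopenia throughout, and febrile neutropenia except where stated. Share = Grade 3 ÷ (Grade 3 + Grade ≥4).

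| Rows used | Olaratumab + doxorubicin | Doxorubicin |
|---|---|---|
| Nonhematologic rows | 29/(29+2) = 94% | 16/(16+3) = 84% |
| Plus febrile neutropenia (7+1; 9+0) | 36/39 = 92% | 25/28 = 89% |
| First row less nausea, diarrhea, constipation, hypokalemia | 24/26 = 92% | 11/14 = 79% |

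The range is 79% to 94%. These are adult adverse events over all cycles, not limited to related events. A patient can appear in several rows, and the entries are not DLTs. The table makes it plausible that Grade 3 events are the larger part of what the threshold governs. It does not estimate the pediatric DLT share.

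**The case against.** **The symbol may have been lost when the file was read.** An underlined > can lose its line, and SAP 5.9.1 shows the same pattern for vincristine (weight >10 kg against ≥10 kg in protocol 7.2.2). The intact ≥3 for thrombocytopenia does not settle the matter, because symbols can be typeset differently. This stands as a reason to check the source PDF first.

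**An informed reader would see a slip.** The Grade 3 exceptions make the intended meaning clear. That is fair, and it is also why the text should not stay as the definition from which the endpoint is derived.

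**Dose decisions do not run on the SAP.** A reader might infer that excess toxicity would go undetected during the trial. If the 12-patient rule did use the SAP threshold, the effect would be large. At an assumed protocol-defined DLT rate of 40%, the binomial chance of 5 or more of 12 is 0.562. If 25% of DLT patients qualified only through a Grade 3 nonhematologic event, the rate would be 0.40 × 0.75 = 0.30 and the chance 0.276; at 50%, the rate would be 0.20 and the chance 0.073. But both shares are assumptions, and protocol 7.2.3 to 7.2.3.2 and SAP 5.13 place these decisions under the protocol. The figures therefore do not describe how doses are chosen in this trial.

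**Grade 3 events are not hidden.** SAP 5.9.2 still reports adverse events by worst grade, related events and events leading to dose modification. The discretionary criterion can bring back individual events, and its own example is a related toxicity forcing withdrawal in Cycle 1, which covers much of the case in step 4. This limits the harm. It also replaces a fixed rule with case-by-case judgment.

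**The ALT/AST exception.** A reader might infer from its broken bullets that the hepatic-injury limit has been dropped. Read in order, the fragments give the protocol's sentence, so the limit is still there.

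**Conclusion.** As printed, the SAP threshold conflicts with the protocol and with the SAP's own exceptions, within one component of the primary endpoint. The consequence is a possible mismatch in reporting. The DLT listing, the DLT-equivalent listing and the DLT-evaluable population could differ from the counts used for dose decisions, and in a 3-patient arm one event is enough to change how the result reads.

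A reader might go further and infer that almost all nonhematologic DLTs would disappear. The documents do not support that. The 79% to 94% is adult and not DLT-specific, and Grade 4-5 events still count (both Grade ≥3 infusion-related reactions in the adult olaratumab arm were Grade ≥4). Discretion also remains.

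No sample size, significance level or power figure depends on this point. The conclusion assumes that the source PDF prints what the extracted text shows, and that the DLT outputs are derived from the SAP wording. If the PDF prints ≥3, the point falls away.

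**What to change.** Check SAP 5.3.1 in the source PDF. If it prints >3, reconcile it with protocol 7.2.3.1 before database lock by carrying the protocol's threshold (Grade ≥3) and its exceptions verbatim into the SAP, with the ALT/AST exception as one sentence. Derive the DLT listing, the DLT-equivalent listing and the DLT-evaluable population from that text. Then compare the resulting DLT counts by cohort and combination arm with those documented at each dose-decision review, and explain any difference in the study report.

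This aligns the SAP with the definition that governs the trial's decisions and does not judge the threshold clinically. The cost is one SAP wording correction and a short reconciliation, with no change for patients or sites.
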